#### 4.1.7 Storage conditions

Drug supplies will be kept in their original packaging and in a secure limited access storage area according to the recommended storage conditions on the medication label. A temperature log must be maintained for documentation.

If the storage conditions are found to be outside the specified range, the Clinical Research Associate (CRA), as provided in the list of contacts in the ISF, must be contacted immediately.

#### 4.1.8 Drug accountability

The Investigator or designee will receive the trial medication delivered by the Sponsor or delegate when the following requirements are fulfilled:

- approval of the CTP by the Institutional Review Board (IRB) / Independent Ethics Committee (IEC)
- availability of a signed and dated clinical trial contract between the Sponsor or delegate and the investigational site
- approval / notification of the regulatory authority, e.g. competent authority (CA)
- availability of the curriculum vitae of the Principal Investigator
- availability of a signed and dated CTP
- availability of the proof of a medical license for the Principal Investigator (if applicable)
- availability of FDA Form 1572 (if applicable)

Trial medication is not allowed to be used outside the context of this CTP. It must not be forwarded to other Investigators or clinics. Trial participants should be instructed to return unused trial medication.

The Investigator or designee must maintain records of the medication's delivery to the trial site, the inventory at the site, the use by each trial participant, and the return to the Sponsor or warehouse / drug distribution center or alternative disposal of unused medication. If applicable, the Sponsor or warehouse / drug distribution center will maintain records of the disposal.

These records will include dates, quantities, batch / serial numbers, expiry ('use-by') dates, and the unique code numbers assigned to the trial medication and trial participants. The Investigator or designee will maintain records that document adequately that the trial participants were provided the doses specified by the CTP and reconcile all trial medication received from the Sponsor. At the time of return to the Sponsor and / or appointed CRO, the Investigator or designee must verify that all unused or partially used trial medication has been returned by the clinical trial participant and that no remaining supplies are in the Investigator's possession.

#### 4.2 OTHER TREATMENTS, EMERGENCY PROCEDURES, RESTRICTIONS

#### 4.2.1 Other treatments and emergency procedures

There are no special emergency procedures to be followed.

Stable doses of concomitant therapies for chronic conditions, for which neither the condition nor the treatment are judged to exclude the trial participant from participation (refer to Section 3.3) are permissible throughout the duration of the trial. Refer to Section 4.2.2.1 for restrictions with respect to statins, NSBBs / carvedilol and anti-viral treatment for HBV. All concomitant therapy should be carefully evaluated by the Investigator and the Sponsor should be contacted when there are questions.

In case of AEs in need of treatment, any concomitant therapy, based on Investigator's judgement, will be permitted. Diagnostics and treatment should be initiated according to local standard of care.

All concomitant therapies will be recorded on the appropriate pages of the eCRF.

Endoscopic variceal ligation (performed according to local guidelines) is permitted during the trial as required. The procedure should be recorded on the appropriate page of the eCRF.

#### 4.2.2 Restrictions

#### 4.2.2.1 Restrictions regarding concomitant treatment

The concomitant therapies mentioned below must not be co-administered with BI 685509 (also refer to Table 1.4.2: 1).

• NO-sGC-cGMP pathway activating therapies like NO-donors (e.g. glyceryl trinitrate, isosorbide di- or mono-nitrate, molsidomine), PDE-5-inhibitors (e.g. sildenafil,

tadalafil, and vardenafil), non-specific PDE inhibitors such as dipyridamole and theophylline, or sGC-stimulators (e.g. riociguat): These restrictions apply from within 5 half-lives after the concomitant therapy has been stopped prior to enrolment (visit 2), until the EoS visit.

- Concomitant therapies with a known risk of Torsade de Pointes: These restrictions apply from screening Visit 1a, until the EoS visit. In the event of temporary concomitant use of such a therapy, the trial medication must be temporarily stopped and can then be re-started at least 5 half-lives after the concomitant therapy with the known risk of Torsade de Pointes has been stopped. Refer to Section 4.1.4.2 for rules for re-starting up-titration in case of interruption of trial medication.
- clinically relevant OATP1B1/3 inhibitors
- clinically relevant concomitant therapies known to inhibit or induce UGT enzymes

In the event of temporary concomitant use of medication that is not permitted, BI 685509 must be temporarily stopped and can be re-started after a period of at least 5 half-lives after the concomitant therapy has been stopped. Refer to Section 4.1.4.2 for rules for re-starting up-titration in case of interruption of BI 685509.

A list to support the identification of the above-mentioned concomitant therapies will be provided in the ISF. The list will not claim completeness.

Furthermore, trial participants who are receiving statins, must be on a stable dose for at least 3 months prior to screening (Visit 1b), with no planned dose change throughout the trial, and trial participants who are receiving NSBBs / carvedilol, must be on a stable dose for at least 1 month prior to screening (Visit 1b), with no planned dose change throughout the trial (refer to Section 3.3.2). In addition, these concomitant therapies should not be initiated during the trial as they will interfere with the efficacy of the trial medication (refer to Section 3.3.4.1).

If receiving anti-viral therapy for HBV, trial participants must be on a stable dose for at least 6 months prior to screening, with no planned dose change throughout the trial.

#### 4.2.2.1.1 Close monitoring for AEs based on concomitant therapy

If a trial participant is taking concomitant therapy that is metabolised by CYP3A4 and/or CYP2C8, which has a narrow therapeutic index and / or is a sensitive substrate, close monitoring for AEs is recommended in this trial (also refer to Table 1.4.2: 1). A list to support the identification of the above-mentioned concomitant therapies will also be provided in the ISF. The list will not claim completeness.

#### 4.2.2.2 Restrictions on diet and lifestyle

Drastic changes of diet and lifestyle in the course of the trial should be avoided. This includes unusual and strenuous exercise for the trial participant (e.g. taking up exercises that put pressure on the abdomen, such as weightlifting).

Alcohol consumption should be avoided throughout the trial; excessive alcohol consumption could lead to hypotension when taken concomitantly with BI 685509.

During the treatment period, trial participants will be asked if they have consumed any alcohol, and where necessary, reminders should be issued to abstain from alcohol consumption.

The requirement for a fasting status upon arrival at clinic visits is as defined in the Flow Chart. Once all visit assessments are complete that require this status, the trial participant may eat as normal.

#### 4.2.2.3 Contraception requirements

Women of childbearing potential (WOCBP) and men able to father a child must use highly effective methods of birth control per ICH M3 (R2) that result in a low failure rate of less than 1% per year when used consistently and correctly. A list of contraception methods meeting these criteria is provided in the trial participant information.

WOCBP (for the definition refer to Section 3.3.2) must be ready and able to use a highly effective method of birth control from the randomisation visit (Visit 2) until 7 days after the last trial medication intake, if their partner is a male able to father a child. No contraceptive is required for the partner of the WOCBP.

Highly effective methods of birth control per ICH M3 (R2) that result in a low failure rate of less than 1% per year when used consistently and correctly include (if local regulations permit):

- combined (oestrogen and progestogen containing) hormonal birth control that prevents ovulation (oral, intravaginal, transdermal)
- progestogen-only hormonal birth control that prevents ovulation (oral, injectable, implantable)
- intrauterine device (IUD) or intrauterine hormone-releasing system (IUS)
- bilateral tubal occlusion

A male trial participant must use a condom with or without spermicide until at least 7 days after last trial medication intake if their sexual partner is a WOCBP, or, be vasectomised with documented absence of sperm in the ejaculate. No contraceptive is required for the male trial participant's partner.

Alternatively, WOCBP and male trial participants able to father a child must abstain from male-female sex. This is defined as being in line with the preferred and usual lifestyle of the trial participant. Periodic abstinence e.g. calendar, ovulation, symptothermal, post-ovulation methods; declaration of abstinence for the duration of exposure to trial medication; and withdrawal are not acceptable.

#### 4.3 TREATMENT COMPLIANCE

Trial participants are requested to bring all remaining trial medication including empty package material with them when attending visits.

Based on tablet counts, treatment compliance will be calculated as shown in the formula below. Compliance will be verified by the CRA authorised by the sponsor or delegate.

Treatment compliance (%) =	Number of actually taken × 100
	Number of which should have been taken as directed by
	the investigator

If the number of doses taken is not between 80-120%, site staff will explain to the trial participant the importance of treatment compliance.

Page 54 of 98

Proprietary confidential information © 2023 Boehringer Ingelheim International GmbH or one or more of its affiliated companies

#### 5. ASSESSMENTS

#### 5.1 ASSESSMENT OF EFFICACY

#### 5.1.1 Hepatic venous pressure gradient

HVPG measurement will be performed at the time points specified in the Flow Chart. Sites must have access to the necessary infrastructure and equipment to measure HVPG (e.g. a hepatic hemodynamic laboratory at their site, or at a nearby institution). Site staff performing the procedure must have sufficient expertise (e.g. performing in the region of 25 or more HVPG measurements per year) with interventional skills and expertise in the reading of pressure tracings, since a local interpretation of the tracing from Visit 1b and EoT visit will be recorded in the trial participant source documents and the eCRF.

The HVPG procedure within the trial will be conducted in a standardised fashion at all sites (for details refer to the HVPG manual in the ISF); training will be provided. Each trial site will be asked to provide acceptable sample HVPG tracing(s) prior to commencing trial participant recruitment if not already provided for Trials 1366-0021 or 1366-0029. Measurements of wedged hepatic venous pressure (WHVP) and free hepatic venous pressure (FHVP) will be performed in triplicate; tracings will be provided to an external Supplier and read centrally by independent expert(s) in PH; the central read will include a subjective assessment of the overall trace quality as well as a read of the relevant pressures. The independent expert(s) will be blinded to the timepoint that the trace relates to. The central read will include the traces from Visit 1b that have also been interpreted locally. The results of the central read will be transferred to the Sponsor and will be considered the official evaluation of the trial. In case of discrepancies between a local interpretation and the central evaluation (e.g. of the Visit 1b tracing), the central evaluation will remain valid.

HVPG measurements should be performed using the same hepatic vein, prior to intake of the trial medication, after an overnight fast, and ideally in the morning. If it is not possible to perform the measurement at Visit 1b in the morning an alternative time of day can be chosen; in this case, a fast of at least four hours is required. The subsequent HVPG measurement must then be performed at approximately the same time of day as the Visit 1b measurement for a single trial participant.

At the EoT visit, the HVPG measurement should be performed on the day of the scheduled visit, or within seven days (if this latter approach is taken, the measurement should still be performed after an overnight fast / after a fast of at least four hours). If this scenario is chosen for an HVPG performed during the treatment period, the morning dose of trial medication can be taken prior to the procedure. In the event of early discontinuation from the trial, refer to Section 6.2.2.1 for guidance regarding the HVPG measurement at the ED visit.

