### 6.2 DETAILS OF TRIAL PROCEDURES AT SELECTED VISITS

At each visit, assessments should be performed as indicated in the Flow Chart and as detailed in Section 5.

In the treatment period, all assessments should be performed before the trial medication is taken. Exceptions to this are post-dose vital signs and ECGs

. Once the trial medication is administered / once all visit assessments are complete that require a fasting status, trial participants may eat as normal

Vital signs measurements should always precede the ECG, and the ECG should always be measured before any blood samples are taken (refer to the Flow Chart and Sections 5.2.2 and 5.2.4).

In the event of force majeure or other disrupting circumstances the visit indicated in Section 6.1 may have to be performed at the trial participant's home, remotely (by phone) or as a combination of home and remote visit. At this visit, the following assessments can be performed at the trial participant's home or remotely:

- concomitant therapy
- IRT call
- dispense trial medication
- train trial participant / provide refresher training / dispense / review results (home BP and HR monitoring;
- all AEs / SAEs / AESIs
- compliance check

Trial medication will not be collected at the visit performed remotely. Instead, the medication should be collected when the trial participant next visits the site, or when a visit is performed at the trial participant's home (see below).

The following assessments can be performed at the trial participant's home:

- anthropometric measures
- vital signs
- physical examination
- resting 12-lead ECG (using a portable ECG machine)

• collect trial medication

If safety laboratory sampling via the central laboratory is not possible from the investigational site in the event of force majeure or other disrupting circumstances (and is instead performed at the trial participant's home), analyses can be performed at a local laboratory. The results of the safety laboratory tests must be transferred to the Investigator who must ensure a medical review and document any clinically relevant safety issues as AEs. For a list of "minimum required safety laboratory parameters" refer to Section 5.2.3 and Table 5.2.3: 2.

All deviations from the original schedule of assessments as defined in the Flow Chart will be documented and the implications considered for the analysis of the trial data.

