### 6.2.2 Treatment period(s)

screening period.

If a trial participant is deemed eligible for the trial following Visits 1a and 1b, the trial participant will be randomised at Visit 2 (Day 1) by using the IRT system. All Visit 2 assessments (refer to the Flow Chart) should have been completed prior to administration of the first dose of trial medication; exceptions are the post-dose vital signs and ECGs Each trial participant can be randomised only once into the trial. The randomised treatment period starts with Visit 2 and ends when a trial participant reaches the EoT visit (refer to the Flow Chart). The last dose of BI 685509 will be administered in the evening of the day before the EoT visit.

Trial participants will be assessed regularly at scheduled visits as specified in the Flow Chart. During the dose titration phase of the treatment period (refer to Section 4.1.4), scheduled visits are more frequent. It is of particular importance that the time window for these visits is adhered to since the trial participant must have taken the preceding dose of BI 685509 for at least seven consecutive days before any up-titration occurs (refer to Sections 4.1.4, 4.1.4.1 and 4.1.4.2). Unscheduled visits may also be arranged where necessary; assessments completed during an unscheduled visit will depend on the circumstances under which the visit was planned, and should be based on Investigator judgement.

should also be reminded to bring **Example 1** and the electronic BP and HR monitoring device with them to each trial visit (refer to Sections 5.2.2.1 and 5.6.1). Refresher training should be provided as required.

At every dispensing visit in the trial (refer to Flow Chart), an IRT call should be made.

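### The timing of the EoT HVPG relative to dosing is not fixed consistently across Protocol 5.1.1 and 6.2, the last-dose rule and the SAP, so the primary endpoint can mix dosing states in the active arm

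*Protocol*

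**What the plan says.** Protocol 5.1.1 gives the general rule: "HVPG measurements should be performed using the same hepatic vein, prior to intake of the trial medication, after an overnight fast". Protocol 6.2 repeats it for the whole treatment period: "In the treatment period, all assessments should be performed before the trial medication is taken". The exceptions visible there are these: "Exceptions to this are post-dose vital signs and ECGs".

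For the EoT visit, 5.1.1 adds flexibility: "the HVPG measurement should be performed on the day of the scheduled visit, or within seven days". It does not say whether the seven days lie before or after the visit. Where that off-day option is used and dosing is still under way, the section permits a different order: "the morning dose of trial medication can be taken prior to the procedure". No minimum or maximum time from dose to procedure appears in the visible text.

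Two other rules bear on this. Under Protocol 6.2.2, "The randomised treatment period starts with Visit 2 and ends when a trial participant reaches the EoT visit". The same section, 4.1.4 and Flow Chart footnotes 3 and 22 put the last dose on the evening before EoT.

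SAP 6.1 reads the allowance as seven days after the scheduled EoT and counts HVPG up to 8 days after the last dose as on-treatment. SAP Table 6.7: 2 opens the extended Week 8 window on Day 51, against a planned Day 57. SAP Section 4 reports that the programme was stopped, that no Week 8 HVPG was collected and that HVPG will only be listed.

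**The concern.** There is one post-baseline HVPG per participant, and the primary endpoint rests on it. Protocol 5.1.1 takes care to match clock time and fasting between the two measurements, but the permission leaves time since dose uncontrolled. The drug is a vasodilator with a peak at 0.5 to 1.0 hour in healthy volunteers (Protocol 1.2.1), and Protocol 3.2 explains BID dosing partly by the wish to avoid high peaks. A reading soon after a dose and one at the end of a dosing interval are therefore taken at different exposures.

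Only the active arm can shift pharmacologically. How many of its participants fall under each timing would depend on how sites schedule the procedure, which is unrelated to the treatment effect being estimated. The SAP text shows no flag or adjustment for time since dose.

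**Working it through.** **1. When can the permission apply?** It needs an HVPG off the visit day, inside the treatment period, on a day with a morning dose.

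- On the EoT day there is no morning dose, because the last dose was taken the evening before.
- After EoT there is no dosing and the treatment period is over.
- Before EoT dosing continues, so the permission can operate.

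The direction of the seven-day window therefore decides the matter. On the SAP 6.1 reading (after EoT) the permission has nothing to act on. On a before-EoT reading it does, and a post-dose HVPG on Days 51 to 56 would fall in the SAP's Week 8 window.

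**2. Time since last dose under each reading.** Inputs: half-life 9 to 15 h (Protocol 1.2.1); evening-to-morning gap of 10 to 12 h (assumed). Fraction left by simple terminal decay = 0.5^(time / half-life).

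| HVPG timing | Hours since dose | Half-lives | Fraction left |
|---|---|---|---|
| EoT day | 10 to 12 | 10/15 = 0.67 to 12/9 = 1.33 | 63% to 40% |
| Before EoT, morning dose taken | not specified; could be at the peak | – | – |
| Latest day under the SAP | 8 × 24 = 192 | 192/15 = 12.8 to 192/9 = 21.3 | under 0.02% |

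Day 8 also lies beyond the protocol's own 7-day residual effect period.

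**3. Peak against average exposure.** From the trial 1366-0020 figures in Protocol 1.2.1, with a 12-hour interval (the protocol doubles 729 to about 1460 for the daily total):

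- Child-Turcotte-Pugh A: 150 / (729/12) = 150 / 60.75 = 2.47
- Child-Turcotte-Pugh B: 122 / (604/12) = 122 / 50.33 = 2.42

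**4. The plan's own operating figure.** Protocol 7.5 uses SD 25 and 20 per arm. SE of the difference = 25 × √(2/20) = 7.906. For a true 20-point effect, (20 − 10)/7.906 = 1.265, and t on 38 df gives 89.3%, as stated. For a true 5 points, (5 − 10)/7.906 = −0.632 gives 26.5%, as stated. Dose timing does not enter this calculation.

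**5. Illustration of a shift, on assumed inputs.** Let a share f of active-arm readings be post-dose, each with an extra transient fall of d points. Mean shift = f × d. Active-arm variance = 25² + f(1 − f)d². SE = √(25²/20 + that variance/20).

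| f | d | Shift | P(observed ≥10), true 5 | P(observed ≥10), true 20 |
|---|---|---|---|---|
| none | – | 0 | 26.5% | 89.3% |
| 0.25 | 5 | 1.25 | 31.9% | 91.8% |
| 0.50 | 10 | 5.0 | 50.0% | 96.6% |

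Neither f nor d comes from the documents. The table shows how sensitive the estimate would be and is not evidence of bias. Readings many days off drug are not in it; if the effect reverses off drug, they would pull the estimate the other way.

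**The case against.** The strongest reply is that 5.1.1 contains a rule with an explicit conditional exception, worded with should and can, so the section does not contradict itself. Protocol 6.2 refers to Section 5 for detail and could be read as deferring to it. Its list of exceptions also breaks off at a gap after ECGs, so an HVPG exception may stand in text that cannot be seen. This is fair: the clash with 6.2 is probable but not proven. What stands is that the exception sets no interval and that it fits neither the after-EoT window nor the last-dose rule.

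Second, a reader might infer that the primary endpoint necessarily mixes pre-dose and near-peak readings. The documents do not support that. Post-dose readings need an HVPG before EoT. The procedure could also fall hours after the morning dose, since it must follow the clock time of Visit 1b. The Cmax ratio is an extreme case from another regimen, and pre-dose readings are not drug-free given the half-life.

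Third, it is tempting to say that post-dose readings would inflate the effect, or that the planned indirect comparison with trials 1366-0021 and 1366-0029 is blurred. No acute HVPG response is reported, and those trials' timing rules are not available; if they match, nothing is blurred. Neither claim can be made from these documents.

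Last, SAP Section 4 leaves no primary estimate to repeat. That is correct for this trial.

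**Conclusion.** The point holds in conditional form. The documents leave open which way the seven-day window runs, and they allow more than one timing of the HVPG relative to intake. On one reading an active-arm value may be post-dose; on the SAP's reading it may come up to 8 days after the last dose; on the EoT day it is end-of-interval. All three could enter the same Week 8 mean unflagged.

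The exposure contrast is supported by the protocol's own figures (peak about 2.4 to 2.5 times average, as an upper case). The effect on HVPG is not: a shift of 1.25 to 5 points, against an SE of 7.9 for the difference and the 10-point and 15-point marks in Protocol 7.5, rests wholly on assumed values of f and d.

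A reader might infer that a reported result is biased. It is not, because no Week 8 HVPG exists. The flaw lies in the plan and matters if its wording is reused.

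**What to change.** - Reconcile the two statements in Protocol 5.1.1 and the rule in 6.2 with the last-dose rule (Flow Chart footnotes 3 and 22, 4.1.4, 6.2.2) and with SAP 6.1. State the direction of the seven-day window and one timing of the HVPG relative to intake, in the same terms throughout. Which timing and which direction is the sponsor's choice.
- Record the clock times of the last intake and of the HVPG, unless the eCRF or the HVPG manual, neither of which is available here, already does so.
- In any analysis of Week 8 HVPG, flag readings taken at another timing and repeat the primary estimate without them.
- For this stopped trial, document the ambiguity and correct the wording before it is reused.

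The cost is a protocol clarification, two time fields and one sensitivity estimate. The downside is somewhat less freedom in scheduling the procedure.
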